16.2 Definition of a Serious Adverse Event

A SAE is defined as an AE meeting one of the following outcomes:

- Death
- Life-threatening event
- Inpatient hospitalization or prolongation of existing hospitalization

- Persistent or significant disability/incapacity or substantial disruption of the ability to conduct normal life functions
- Congenital anomaly or birth defect

Any other important medical event that may not result in one of the above outcomes may be considered a SAE when, based upon appropriate medical judgment, the event may jeopardize the participant and may require medical or surgical intervention to prevent one of the outcomes listed above.

A life-threatening AE is any AE that places the subject, in the view of the investigator, at immediate risk of death from the AE as it occurred. It does not include an AE that, had it occurred in a more severe form, might have caused death.

16.3 Events of Clinical Interest

The following are considered events of clinical interest (ECIs) if they occur after dosing, and must be reported by the site when it becomes aware of the ECI:

- ALT or AST $> 8 \times$ the upper limit of normal (ULN), confirmed by repeat testing
- ALT or AST $> 5 \times$ ULN for more than 2 weeks or accompanied by total bilirubin $> 2 \times$ ULN

16.4 Overdose

This refers to the administration of a quantity of a medicinal product given per administration or cumulatively, which is above the maximum recommended dose according to the authorized product information.

An overdose can occur if a subject has taken, accidentally or intentionally, a drug administered in a dose exceeding the protocol-specified dose. An overdose must be reported within 24 hours of the site becoming aware of the overdose if such overdose occurs with an associated SAE. If an overdose occurs without an associated SAE, the overdose must be reported within 5 working days and documented in the subject diary and in the subject medical record.

16.5 Pregnancy

Female subjects who become pregnant should be immediately discontinued from the study and followed up to determine the outcome of the pregnancy. The pregnancy must be reported to the Sponsor within 24 hours of the site becoming aware of the pregnancy using the pregnancy reporting form. If the pregnancy ends for any reason before the anticipated date, the investigator should notify the Sponsor. At the completion of the pregnancy, the investigator will document the outcome of the pregnancy. The pregnancy itself is not to be reported as an AE or SAE. If the outcome of the pregnancy meets the criteria for immediate classification as an SAE (i.e., postpartum complication, spontaneous abortion, stillbirth, neonatal death or congenital anomaly), the investigator should follow the procedures for reporting an SAE.

16.6 Unexpected Adverse Event

An AE is considered “unexpected” if it is not listed in the IB or is of greater specificity or severity than those that have been observed with the particular study drug being tested. For example, under this definition, hepatic necrosis would be unexpected (by virtue of greater severity) if the IB referred only to elevated hepatic enzymes or hepatitis. Similarly, cerebral thromboembolism and cerebral vasculitis would be unexpected (by virtue of greater specificity) if the IB listed only cerebral vascular accidents. “Unexpected,” as used in this definition, also refers to AEs that are mentioned in the IB as occurring with a class of drugs or as anticipated from the pharmacological properties of the drug but are not specifically mentioned as occurring with the particular drug under investigation.

16.7 Study Monitoring

Study progress will be monitored by the Sponsor or its representative as frequently as necessary to ensure adequate and accurate data collection, protocol compliance, and study conduct in accordance with accepted regulatory requirements. The principal investigator (PI) must make all the subject data available to the monitor for review during the planned site monitoring visits. Arrangements for monitoring visits will be made in advance, except in emergency cases.

16.8 Grading of Adverse Events

The severity (or intensity) of an AE refers to the extent to which it affects the subject’s daily activities and will be classified by the investigator as mild, moderate or severe using the following criteria:

- **Mild:** Awareness of sign or symptom, but easily tolerated. Not likely to require medical attention.
- **Moderate:** Discomfort enough to cause some interference with daily activity. May require medical intervention.
- **Severe:** Intense enough to disrupt daily activities. Likely requires medical intervention.

Clarification of the difference in meaning between “severe” and “serious”

The term “severe” is often used to describe the intensity (severity) of a specific event (as in mild, moderate or severe myocardial infarction); the event itself, however, may be of relatively minor medical significance (such as severe headache). This is not the same as “serious”, which is based on the outcome or action criteria usually associated with events that pose a threat to life or functioning. Seriousness (not severity) serves as a guide for defining regulatory reporting obligations.

16.9 Causality Assessment

The investigator will assess causality (i.e., whether there is a reasonable possibility that the study drug caused the event) for all AEs and SAEs. The relationship will be characterized using the following classification:

- **Related:** The temporal relationship of the AE with the study drug makes causality possible and as likely or more likely than due to another cause such as other drugs, a surgical intervention or an underlying disease.
- **Not related:** The temporal relationship of the AE with the study drug makes causality improbable and can be due to another cause such as other drugs, a surgical intervention or an underlying disease.

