16.10 Adverse Event Collection Timeframe

AEs and SAEs will be recorded from the time the ICF is signed (Screening) through Week 24 (TOC). New AEs starting after Week 24 and until Week 36 will be recorded only if they led to the use of other antifungal medications or topical vaginal treatment, or if they are a vaginal bacterial or parasitic infection, or if they are deemed related to the previously administered study drug.

All AEs reported by the subject or observed by members of the clinical staff will be evaluated by the PI or qualified designee. The PI will attempt, if possible, to establish a diagnosis based on presenting signs and symptoms. The nature of the AE, time of onset relative to study drug administration, duration, severity, and relationship to treatment should be determined. Details of any corrective treatment must be recorded in the eCRF. The PI will determine whether any changes have occurred in baseline signs and symptoms. All AEs and SAEs will be collected in the eCRF.

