16.11 Serious Adverse Event Reporting Requirements

All SAEs must be reported within 24 hours of the site becoming aware of the SAE. Any event that is serious, study drug-related, and unexpected as assessed by the medical monitor or the Sponsor will be submitted to the regulatory authorities in accordance with national regulatory laws and regulations. The PI will be responsible for reporting all SAEs that require reporting to the local or central Institutional Review Board/Ethics Committee (IRB/EC) in accordance with its regulations and guidelines.

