18.2 Analysis Populations

The study populations to be used in the analyses are defined as follows:

- **Intent-to-Treat (ITT) Population:** All randomized subjects.

- **Modified Intent-to-Treat (mITT) Population:** All randomized subjects who have a confirmed mycological culture for yeast at Screening and a negative culture for yeast at Baseline (Day 1).
- **Per-Protocol (PP) Population:** All ITT subjects who did not have major protocol deviations likely to affect study efficacy and who have available data at the TOC visit. Note that subjects who discontinue due to a study-drug-related AE will be classified as failures for the analyses of efficacy under the PP population.
- **Safety Population:** All randomized subjects who received at least one dose of study drug (ibrexafungerp or placebo) and who have at least one post-Baseline (Day 1) evaluation.

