### **9.1.2. Relationship of Adverse Events to Study Treatment**

A summary of TEAEs by relationship to study treatment will be presented in a table. The investigator will provide an assessment of the relationship of the event to the study treatment. The possible relationships are "Not Related" and "Related". In the TEAE relationship table, if subject reports multiple occurrences of the same TEAE, only the most closely related occurrence will be

presented. Treatment-emergent AEs that are missing a relationship will be presented in the summary table as “Related” but will be presented in the data listing with a missing relationship. Percentages will be calculated based on the number of subjects in the safety set.

The TEAE data will be categorized and presented by SOC, PT, and relationship in a manner similar to that described in Section 9.1.1.

Additionally, the TEAE data will be categorized and presented by SOC, PT, relationship, and duration (1 day, 2 days,  $\geq 3$  days). The duration is calculated as the TEAE end date minus the TEAE start date, then add 1 day. At each combination level of relationship and duration, a subject is counted once if the subject reported one or more events. Percentages will be calculated out of the number of subjects in the safety set.

Treatment-emergent SAEs by relationship to study treatment will also be presented in a table. Treatment-emergent SAEs that are missing a relationship will be presented in the table as “Related” but will be presented in the data listing with a missing relationship.

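### The two causality labels in Protocol Section 16.9 do not follow that section's own reasonable-possibility standard, and some adverse events fit neither label

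*Protocol*

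**What the plan says.** Protocol Section 16.9 opens with one standard: the investigator assesses "whether there is a reasonable possibility that the study drug caused the event". Two labels follow, both tied to the timing of the event relative to study drug. Related applies when that timing "makes causality possible and as likely or more likely than due to another cause". Not related applies when it "makes causality improbable and can be due to another cause such as other drugs", with surgery and underlying disease as further examples. SAP Section 9.1.2 confirms that these are the only two values, and Protocol Section 21.3.12.1 carries the scheme into the nested sub-study.

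The label is used in several places:

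- **New adverse events after Week 24.** Protocol Sections 14.22 and 16.10 limit these to listed routes, one being "or if they are deemed related to the previously administered study drug".
- **Concomitant medication after TOC.** Protocol Sections 13.1 and 14.21 include treatments for a drug-related event among the few that are still recorded.
- **Per-protocol efficacy.** Under Protocol Section 18.2 and SAP Section 4.3, "subjects who discontinue due to a study-drug-related AE will be classified as failures" in that population.
- **Tables.** SAP Sections 9.1 to 9.1.3 present treatment-related TEAEs and serious events, and cross-classify TEAEs by relationship.
- **Sub-study.** After early termination, Protocol Section 21.3.7.3 requires further follow-up only for an ongoing drug-related event.

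The SAP (Sections 9.1.1 and 9.1.2) counts a missing relationship as Related in the tables.

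**The concern.** A two-value classification works only if every event belongs to exactly one value and both values answer the question asked. Here the question is whether a causal role is reasonably possible. The Related definition asks for more, namely at least parity with any other cause. The Not related definition is not its complement, because it requires improbability. An investigator who follows the opening sentence and one who follows the definitions can therefore label the same event in opposite ways, and no other section says how to break the tie.

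The situation is not far-fetched. Section 16.9 names other drugs as a competing cause. Rescue therapy is a dose of fluconazole (Section 14.18.3), and study drug continues after a recurrence. Section 7.1 reports gastrointestinal events as the most common with ibrexafungerp. A gastrointestinal complaint soon after both drugs could reasonably be judged possible for study drug but likelier for the rescue dose.

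At stake are consistency between sites in the treatment-related tables and, after Week 24, whether some events are recorded at all.

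**Working it through.** The plan gives no figure for this point, so the check is logical. The definitions are set against each possible judgement, and the uses of the label are then traced.

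**Step 1: do the two labels cover every case?**

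| Drug causality | Other cause | Meets Related? | Meets Not related? |
|---|---|---|---|
| (a) Possible | No likelier than the drug | Yes | No |
| (b) Possible, not improbable | Likelier than the drug | No: parity fails | No: not improbable |
| (c) Improbable | Available | No | Yes |
| (d) Improbable | None identifiable | No | No: no other cause |

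Cases (b) and (d) have no label.

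**Step 2: how do the labels compare with the opening standard?** A case (b) event can still be a reasonable possibility, since having a likelier rival does not make a cause unreasonable. Related is therefore stricter than the question it is meant to answer.

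**Step 3: how wide could the gap in case (b) be?** The documents attach no probabilities to these words. As an illustration only, assume that the drug and one rival are the sole explanations, so that parity means at least 50%. Assume also that improbable means below some limit between 5% and 30%. The unlabelled band then spans 50 − 5 = 45 percentage points at one end of that range and 50 − 30 = 20 at the other. This is a width on the probability scale, not a share of events.

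**Step 4: what depends on the label, and what does not?**

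| Depends on the label | Does not depend on it |
|---|---|
| New events after Week 24, unless another listed route applies (16.10) | All adverse events through Week 24 (16.10) |
| Some concomitant medication after TOC (14.21) | Site reporting of every serious event within 24 hours (16.11, 16.13) |
| Treatment-related TEAE and serious-event tables (SAP 9.1 to 9.1.3) | Overall TEAE tables by arm (SAP 9.1.1) |
| Per-protocol failure rule (18.2; SAP 4.3) | Primary ITT analysis, where early termination before TOC is failure whatever the reason (SAP 8.1) |
| Sub-study follow-up after early termination (21.3.7.3) | Sample size and power |

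**Step 5: does the missing-value rule close the gap?** Only in the tables, and only when the field is left blank. It does not reach an event entered as Not related, and it does not govern what is recorded after Week 24.

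**The case against.** The strongest reply is that this is loose drafting with little consequence. The opening sentence states what the assessment means and can guide a doubtful case. Blank entries already count as Related. Everything is recorded through Week 24, and all TEAEs are compared by randomised arm without using the label. After Week 24 the exposure is narrow: the last dosing day is Day 140 and TOC is Day 168, so such events begin about 168 − 140 = 28 days or more after the last dose, and other recording routes remain. The per-protocol analysis is only supportive.

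Most of this stands and limits the importance of the point. It does not remove the contradiction, because no text says that the opening sentence overrides the definitions, and a doubtful event entered as Not related stays there.

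The documents do not support four stronger readings that a reader might infer:

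- **Related means more likely than not.** The wording accepts equal likelihood.
- **Every doubtful event ends up as Not related, so drug-related events are under-reported.** On a literal reading Not related is equally unavailable, so the direction for any one event is uncertain.
- **The investigator's label controls expedited reporting.** Sites report all serious events regardless of causality, and regulatory submission concerns "Any event that is serious, study drug-related, and unexpected as assessed by the medical monitor or the Sponsor". The investigator's label need not be decisive, although the protocol gives those assessors no separate causality definition.
- **The Phase 2b figures in Section 7.1 size the loss.** Nausea was 10% on the 600 mg dose and 6% on fluconazole, an excess share of (10 − 6)/10 = 40%. An arm-level excess says nothing about a single event, fluconazole is an active drug rather than background, and the counts are 3 and 2 subjects. With one fluconazole case fewer (one subject is about 3%), the share becomes (10 − 3)/10 = 70%.

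**Conclusion.** The point holds as an internal contradiction in Section 16.9. The labels are not exhaustive, and Related is stricter than the standard stated at the head of the same section. Some events that meet that standard can be entered as Not related, and investigators can differ on the same event. The effect is confined to the label-dependent items listed in the working. The one place where the record itself, and not just its classification, can be lost is new events after Week 24.

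The conclusion rests on reading the definitions as written and on the SAP's two permitted values. How often the gap will arise cannot be estimated from the documents. The correction is worth making because it is cheap and removes a rule that contradicts itself, not because any efficacy conclusion is at risk.

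**What to change.** In Section 16.9, make the two labels the yes and no answers to the section's own question:

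- *Related: there is a reasonable possibility of causation by study drug.*
- *Not related: there is no reasonable possibility of causation by study drug.*

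The comparison with other causes should leave the definitions. It can remain as something to weigh when deciding what is reasonably possible. Put the same wording in the eCRF completion guide. The sub-study then inherits it through Section 21.3.12.1, and the SAP's two values need no change. The new wording also sits well with the SAP's practice of counting a missing relationship as Related.

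The cost is a wording change to the protocol and the eCRF guide. The reported rate of treatment-related events may rise slightly.

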16.10 Adverse Event Collection Timeframe

AEs and SAEs will be recorded from the time the ICF is signed (Screening) through Week 24 (TOC). New AEs starting after Week 24 and until Week 36 will be recorded only if they led to the use of other antifungal medications or topical vaginal treatment, or if they are a vaginal bacterial or parasitic infection, or if they are deemed related to the previously administered study drug.

All AEs reported by the subject or observed by members of the clinical staff will be evaluated by the PI or qualified designee. The PI will attempt, if possible, to establish a diagnosis based on presenting signs and symptoms. The nature of the AE, time of onset relative to study drug administration, duration, severity, and relationship to treatment should be determined. Details of any corrective treatment must be recorded in the eCRF. The PI will determine whether any changes have occurred in baseline signs and symptoms. All AEs and SAEs will be collected in the eCRF.

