16.0 Safety Assessments and Monitoring

16.1 Definition of an Adverse Event

An AE is any untoward medical occurrence associated with the use of a drug in humans, whether or not considered drug related. An AE can therefore be any unfavorable and unintended sign (including an abnormal laboratory finding), symptom or disease temporally associated with the use of a study drug/study intervention, whether or not related to the study drug/study intervention.

Any laboratory abnormality that is deemed to be clinically significant in the opinion of the investigator will be considered an AE and should be recorded in the eCRF, whether or not it is related to the study drug.

Stable chronic conditions that are present prior to clinical trial enrollment and do not worsen are not considered AEs and will be accounted for in the subject's medical history.

The following can be considered AEs:

- An exacerbation of a pre-existing illness
- An increase in frequency or intensity of a pre-existing episodic event or condition
- A condition detected or diagnosed after the initiation of treatment with study medication, even though it may have been present prior to the start of the study
- Continuous persistent disease or symptoms present at Baseline (Day 1) that worsen after signing the informed consent or following the initiation of treatment with study medication

The following are **not** considered AEs:

- Medical or surgical procedures (e.g., surgery, endoscopy, tooth extraction or transfusion); the condition that leads to the procedure is an AE
- Pre-existing disease or conditions present or detected at the start of the study that do not worsen
- Situations where an untoward medical occurrence has not occurred (e.g., hospitalizations for cosmetic surgery or elective surgery or social/convenience admissions)
- The disease being studied, or signs or symptoms associated with the disease, unless more severe than expected for the subject's condition or a worsening of the disease being studied

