16.13 Serious Adverse Event Reporting – Procedures for Investigators

Initial Reports and Follow-Up SAE Reports: To report an SAE, the SAE eCRF form within the Electronic Data Capture (EDC) system must be completed. All SAEs, whether or not deemed drug-related or expected, must be reported by the investigator or qualified designee within 24 hours of first becoming aware of the event. The investigator/qualified designee will enter the required information regarding the SAE into the appropriate form, which will automatically result in distribution of the information to the appropriate sponsor contact.

If the EDC system is temporarily unavailable (> 24 hours), the event, including the investigator-determined causality to study drug, should be reported via a paper back-up SAE form to PPD Safety Surveillance (contact information, i.e., e-mail or fax will be available on the SAE form).

Upon return of the availability of EDC system, the SAE information must be entered into the EDC system as soon as possible. The SAE form within the EDC system must be updated within 24 hours of knowledge/receipt of SAE follow-up information.

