### **9.1.1. Treatment-Emergent Adverse Events**

Summaries of the total number of TEAEs and the number and percentage of subjects with at least one TEAE will be provided by treatment and study period (prior or on TOC visit, after TOC visit but prior or on EOFU visit, and entire study). Treatment-emergent AEs will be presented by SOC and PT. At each level of subject summarization, a subject is counted once if the subject reported one or more events. Percentages will be calculated out of the number of subjects in the safety set.

The summary of TEAEs will be presented in alphabetical order of SOC. Within each SOC, PTs will be sorted in descending order from the PT with the highest total frequency (that is, summed across all treatment groups) to the PT with the lowest total frequency. If the total frequency for any two or more PTs is equal, the PTs will be presented in alphabetical order.

The summarization described above will also be repeated for the following:

- Serious Adverse Events;
- Treatment-Related Adverse Events;
- Treatment-Related Serious Adverse Events;
- Adverse Events Leading to Dose Interruption.

The adverse events with a missing relationship will be considered as "Treatment Related" in the tables.

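### After Week 24 the protocol's AE recording rule conflicts with its all-SAE reporting rule, and the SAP's post-TOC and entire-study all-cause tables do not allow for the change in collection

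*Protocol*

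**What the plan says.** Protocol 16.10 sets the period of full collection: "AEs and SAEs will be recorded from the time the ICF is signed (Screening) through Week 24 (TOC". For later events it says "New AEs starting after Week 24 and until Week 36 will be recorded only if they led to the use of other antifungal medications". Events that needed a topical vaginal product count in the same way, and the remaining categories are given as: "or if they are a vaginal bacterial or parasitic infection, or if they are deemed related to the previously administered study drug". Section 14.22 repeats the filter. Neither section makes an exception for serious events, and 16.2 places SAEs inside the AE definition: "A SAE is defined as an AE meeting one of the following outcomes".

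Section 16.13 says "All SAEs, whether or not deemed drug-related or expected, must be reported by the investigator or qualified designee within 24 hours", counted from awareness, using the SAE form in the EDC system. Section 16.11 sets the same clock for every SAE. Neither gives an end date. Section 16.10 itself closes by sending all AEs and SAEs to the eCRF.

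Protocol 9.3 measures safety at TOC (Week 24), which is where full collection ends. SAP Section 11 removes that limit so that all captured safety data are analysed. SAP 9.1 and 9.1.1 then summarise events by treatment and "study period (prior or on TOC visit, after TOC visit but prior or on EOFU visit, and entire study". The 9.1.1 tables cover TEAEs and are repeated for SAEs, treatment-related events and treatment-related SAEs; the 9.1 overview adds AEs leading to death. For the denominator, 9.1.1 says "Percentages will be calculated out of the number of subjects in the safety set". The SAP does not mention the narrower collection after Week 24.

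**The concern.** There are two linked problems.

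The first is a conflict between recording rules. A site that follows 16.10 would leave out an unrelated serious event in follow-up; a site that follows 16.13 would enter it. Sites may differ, and an empty post-TOC SAE cell could not be read as showing that no event occurred.

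The second concerns the tables. Once the SAP dropped the TOC limit, its entire-study tables joined 24 weeks of full collection to 12 weeks of filtered collection without saying so. All-cause rates come out too low, and drug-related events make up too large a share of the late events shown. The post-TOC percentages also divide by subjects who never entered follow-up, which lowers them further, and by different amounts if dropout differs between arms.

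**Working it through.** The documents state no figure for this point, so there is none to reproduce. The check is a comparison of the texts, followed by arithmetic on scale.

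**Step 1. Apply each rule to one case: a hospitalisation starting at Week 30, judged unrelated, with no antifungal or topical vaginal treatment.**

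| Place | Applies at Week 30? | Result |
|---|---|---|
| Protocol 16.10 and 14.22 | Yes, as a new AE after Week 24 | Not recorded; no category fits |
| Protocol 16.2 | Yes | An SAE is an AE, so the filter covers it |
| Protocol 16.11 and 16.13 | Yes, no end date | Reported within 24 hours on the SAE form |
| Protocol 16.10, closing sentence | Yes | Collected in the eCRF |
| SAP 9.1.1, SAE table after TOC | Yes | Counted only if the site followed 16.13 |

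Two nearby rules also set no Week 24 limit. Protocol 16.3 asks for events of clinical interest whenever they occur after dosing. The sub-study (21.3.12.3) records AEs and SAEs to its last visit without a filter.

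**Step 2. Size of the filtered window.** Follow-up is 12 of 36 post-randomisation weeks: 12/36 = 33%. With the planned 240 subjects and no dropout, exposure is 240 × 12/52 = 55.4 person-years, or 27.7 per arm.

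**Step 3. Unrelated SAEs outside 16.10.** The documents give no SAE rate, so these rates are assumptions. Expected number = 55.4 × rate; chance of at least one = 1 − exp(−expected number).

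| Assumed rate per 100 person-years | Expected, both arms | Chance of at least one |
|---|---|---|
| 1 | 0.6 | 43% |
| 2 | 1.1 | 67% |
| 4 | 2.2 | 89% |

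**Step 4. Effect on the entire-study table for unrelated non-serious AEs that meet no filter category.** Assume a constant rate r per person-year and no dropout. The true proportion with at least one event is 1 − exp(−r × 36/52). Under the filter only 24 weeks count: 1 − exp(−r × 24/52). The proportion with an unrecorded event in follow-up is 1 − exp(−r × 12/52).

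| Assumed r | True, 36 weeks | Shown as entire study | Unrecorded event in follow-up |
|---|---|---|---|
| 0.5 | 29.3% | 20.6% | 11% |
| 1 | 50.0% | 37.0% | 21% |
| 2 | 75.0% | 60.3% | 37% |

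**Step 5. Denominator.** Percentage shown = true rate × fraction entering follow-up. With an assumed true post-TOC rate of 10% in both arms, and 10% and 20% of subjects not entering follow-up, the table shows 0.10 × 0.90 = 9.0% and 0.10 × 0.80 = 8.0%. With everyone entering, both arms show 10%.

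**The case against.** The best defence is that 16.10 sets the window while 16.11 and 16.13 only set the clock inside it. That reading is possible, but no section states it, and 16.13 expressly covers events not thought drug-related.

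The second defence is that narrower collection off treatment is a deliberate choice. This stands. The filter closely matches the post-TOC concomitant-medication rule in 13.1 and 14.21. The last dose is at Week 20, and the SAP already plans a separate table up to TOC, with full collection over all dosing. Safety analysis is descriptive (18.7.2). Nothing here asks for full collection of non-serious AEs in follow-up.

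Third, a fixed Safety Set denominator follows the SAP's general rule in Section 4, and TOC completion is reported under 5.1. That is fair; the denominator effect is small at the dropout assumed above.

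A reader might also infer more than the documents support:

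- **That the retained vaginal infections track efficacy.** They are bacterial or parasitic, and 14.18.2 lists them as AEs separate from recurrence. Only the antifungal or topical-treatment category has a link to recurrence.
- **That recurrences entered as AEs will inflate placebo rates.** Section 16.1 lists among non-AEs "The disease being studied, or signs or symptoms associated with the disease, unless more severe than expected", and 14.18.2 says how treated episodes are classified. A large imbalance would need sites to set both aside.
- **That recurrences are therefore never AEs.** Section 16.1 keeps an exception for disease more severe than expected or worsening, and that exception must stay.
- **That late deaths would be invisible.** Section 11.3 requires the reason for withdrawal in the eCRF, and SAP 5.1 includes death among the reasons summarised. A late SAE is lost only where a site applies 16.10 over 16.13.

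**Conclusion.** The point holds. As written, 16.10 and 14.22 contradict 16.11 and 16.13 for SAEs after Week 24 that fit none of the retained categories. The SAP's all-cause TEAE tables for the post-TOC period and the entire study are understated, because a third of the 36 weeks is filtered and the SAP does not allow for it. The SAE tables for those periods are understated to the extent that sites follow 16.10.

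The likely number of affected SAEs is small: about 0.6 to 2.2 across both arms at assumed rates of 1 to 4 per 100 person-years, with 240 subjects and no dropout. The gap for non-serious events is larger: 50.0% true against 37.0% shown at an assumed one unrelated event per person-year.

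The limits are clear. Tables up to TOC are unaffected. Events judged drug-related are collected in both periods, so the filter does not bias those tables, although the post-TOC denominator still applies to them. The documents give no basis for saying that the filter favours either arm.

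**What to change.** 1. **Protocol 16.10 and 14.22.** Reconcile them with 16.11 and 16.13 by stating that all SAEs and deaths, regardless of causality, are recorded in the eCRF through Week 36. The filter can remain for non-serious AEs. Leave 16.1 and its exception unchanged.
2. **SAP 9.1 and 9.1.1.** Name first dose to TOC as the comparative all-cause TEAE table. Show post-TOC events separately, labelled as restricted collection, with subjects who entered follow-up as the denominator and that group defined in the SAP. Limit entire-study tables to SAEs, deaths and treatment-related TEAEs, so that late drug-related events are kept. Note the collection rule in SAP Section 11 beside the removal of the TOC limit.

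The cost is wording in both documents, a few more SAE forms and one changed denominator. No visits are added: Table 2 already schedules AE monitoring at the Week 28 and 32 calls and the Week 36 visit.
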